**IBT to Treat Irritability.** Prior work suggests, but has not established, that irritability may be reduced by training against hostile interpretation bias. Interpretive biases are well-established targets of training programs to treat anxiety and depression, two phenomena with which irritability shares genetic, concurrent, and longitudinal associations. Indeed, irritability and anxiety share similar cognitive biases towards facial expressions signifying social threat. Following prior work in depression, an IBT program was developed to reduce anger and aggression with the presumptive target being hostile interpretation bias. IBT uses face emotions, mixtures of happy and angry expressions, as social stimuli (Figure 1). In two randomized controlled trials, two daily sessions of sham versus active computer-based training shifted participants' judgments of ambiguous facial expressions from "angry" to "happy." Active training was associated with decreased anger in healthy young adults and aggression in youth with conduct problems. In a small, open trial ( $N=14$ ), colleagues and I showed that four daily sessions of IBT was associated with reduced irritability in youths with DMDD. Both trials demonstrated a robust change in interpretation bias as measured by the same face-set stimuli used in training. However, there is no evidence that IBT results in generalized changes of hostile interpretation bias, i.e.

**Figure 1.** An interpretation bias training session. First the balance point is assessed. It is the point on a continuum of happy to angry faces where a person's judgments of them switch from predominantly happy to angry. Training sessions provide feedback on judgments that encourage happy judgments of two ambiguous faces previously judged as angry. Training effects are measured by another balance point assessment.

changes in interpretation bias to other face-set stimuli or other measures of hostile interpretation bias. Still, the effect of the training on symptoms related to hostile interpretation bias is compelling and supports further investigation to determine whether IBT reduces its intended target, hostile interpretation bias (hypothesis 1.2), under the NIMH plan for treatment development (Strategy #3.1).

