## Summary

Prior work strongly suggests an association between irritability and hostile interpretation bias (hypotheses 1.1). Earlier work also suggests IBT may reduce hostile interpretation bias, but only when hostile interpretation bias is measured by the same stimuli used in IBT. This study will assess whether a reduction in hostile interpretation bias generalizes (hypothesis 1.2). Prior work suggests, but has not proven that that irritable youth are slow to learn benign interpretations (hypothesis 2.1) and this is mediated by neural response (hypotheses 2.2 and 2.3).

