For those randomized to out-of-scanner conditions, this visit will occur at the Anschutz Medical Campus Gary Pavilion outpatient psychiatric clinic in a private laboratory room. For those randomized for in-scanner conditions, this visit will occur at the Anschutz Medical Campus Brain Imaging Center (BIC). See COMIRB Application, Section Q, for facilities description. See COMIRB Application, Section J, for MRI safety screening procedures.

At the start of the second visit, adolescents will complete an out-of-scanner interpretation bias assessment on a laptop approximately 3 minutes. Adolescents will then complete an in- or out-of-scanner session of active or sham IBT depending on their allocation (approximately 18 minutes). Immediately after IBT, all adolescents will complete an out-of-scanner interpretation bias assessment presented on a laptop. To assess whether training on the ‘prototypical’ male face-set generalizes to other face-sets, adolescents will complete another interpretation bias assessment designed by [name] and colleagues. It has nearly identical trial structure, but uses four NimStim^63 face-identities that differ in gender and race along the same 15-morph continuum and takes 7.5 minutes to complete. Details of these cognitive tasks and image acquisition are provided below.

At the end of this session, we will give participants a RedCap link and log on instructions. We will ask them to complete an online assessment via RedCap in one week. For those who opt against completing their assessment online, we will give them a packet of assessment measures.

Based on pilot experience at the NIMH, I anticipate the visit length for each out-of-scanner arm to be one hour long and the visit length for each in-scanner arm to be two hours.

*While COVID-19 safety procedures are still in effect on the Anschutz Medical Campus, the following adaptations will be made to Training, Visit 2, Up to Day 7:*

Adolescents and their caregivers will be screened for COVID-19 symptoms the day before their scheduled Visit 2 in accordance with CHCO site standards or BIC standards, depending on randomization.

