#### Assessment, Online, About one Week after IBT

The day before it is due, Drs. [name] or [name] will call the family to remind them to complete their follow up assessment. Drs. [name] or [name] will ask parents, “Do you have new concerns about your child since the training session?” The scales included in this assessment are the same as in the first visit, excluding the Tanner Scale. In addition, during the post-training assessment, adolescents will complete the Intent Attributions

Questionnaire, another measure of interpretive bias (10 minutes). Because this scale can only be administered every six months, we are limited to a post-training assessment only. Though we cannot assess IBT-associated changes in ratings on this scale, we can assess for both associations with irritability as well as differences in hostile attribution bias between those in the sham vs. active IBT groups.

For online assessments, adolescents will complete the following self-report forms:

1. Short Moods and Feelings Questionnaire (MFQ; 2 minutes)
2. Screen for Childhood Anxiety Related Emotional Disorders (SCARED; 8-10 minutes minutes)
3. Affective Reactivity Index (ARI; 2 minutes)
4. State-Trait Anger Expression Inventory-2 Child and Adolescent (STAXI-2 C/A; 5-8 minutes)
5. Intent Attributions Scale (10 minutes)

During this visit, caregivers will complete the following parent-report forms:

1. ARI (2 minutes)
2. SCARED (8-10 minutes)
3. MFQ (2 minutes)
4. SNAP-IV, items 1-40 only, (5-10 minutes)

Based on conducting similar online assessments at the NIMH, I anticipate this assessment to take approximately ½ hour for the adolescent and 15 minutes for their caregiver.

*Interpretation Bias Training Session.* The interpretation bias training session consists of an assessment of interpretation bias followed by trainings to shift the bias. A training session is depicted in Figure 1.

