Hypothesis 1.2: Active but not sham, IBT will reduce hostile interpretation bias. Mixed-effects linear regression with balance point (interpretation bias) as a dependent variable and training condition (active vs. sham), and time of interpretation bias assessment (pre- or post-training) as independent variables of interest and person as a grouping variable and random effect. Similar models will test for group differences in active or sham IBT on other measures of hostile interpretation bias after training.

Hypothesis 2.1: The rate of learning new associations to ambiguous faces training will be associated with baseline irritability. For those in the active condition, linear regression will test the association between pre-training ARI (irritability) and learning rate to reversal feedback of baseline angry judgments to the two ambiguous morphs.

Hypotheses 2.2 and 2.3: Active, but not sham, IBT will evoke greater neural response in threat-learning systems. For each person, learning will be modeled with regressors coding the “value” or trialwise likelihood that a participant considers the morph to be angry. The amplitude of BOLD %signal change (activity) or amygdala covariance (generalized psychophysiological interaction; connectivity) related to these regressors represents neural response to value. Critically, these regressors represent learning itself where value is changing towards benign judgments in the active training condition to two ambiguous morphs. These will be carried forward to the second level mixed-effects linear models of the effects of morph by pre-training ARI by training condition. A voxel-wise threshold of  $p < .001$ , whole-brain, cluster corrected to  $p < .05$  via permutation testing or Monte Carlo simulation as appropriate, will be used to identify significant associations. A three-way interaction of change in value by morph by training condition will indicate neural areas where learning is influenced by irritability in active but not sham training of reversals of ambiguous morphs. In addition, our *a priori* identification of the likely role of the amygdala, OFC, and ACC justifies follow-up region-of-interest analyses of mean activity or connectivity extracted from these areas with the same omnibus mixed-effects model.

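### The untrained-face (NimStim) task is given only after training, so the trial can compare arms on those faces but cannot measure a reduction or show which arm moved

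*Combined protocol and SAP*

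**What the plan says.** The Background section (IBT to Treat Irritability) reports that earlier trials showed a robust shift on the same faces used in training, but that "there is no evidence that IBT results in generalized changes of hostile interpretation bias". The Summary closing that section makes this the new question: "This study will assess whether a reduction in hostile interpretation bias generalizes (hypothesis 1.2". Hypothesis 1.2 in the Specific Aims is arm-specific: bias falls under active training and does not fall under sham.

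The Visit 2 text (Training, Visit 2, Up to Day 7) sets this order:

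- Before training: "At the start of the second visit, adolescents will complete an out-of-scanner interpretation bias assessment on a laptop approximately 3 minutes".
- IBT, active or sham, about 18 minutes.
- After training: "Immediately after IBT, all adolescents will complete an out-of-scanner interpretation bias assessment presented on a laptop".
- Then, to see whether training on the prototypical faces "generalizes to other face-sets, adolescents will complete another interpretation bias assessment designed by" another research group, a task on four NimStim identities "along the same 15-morph continuum and takes 7.5 minutes to complete".

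Section F (Data Analysis Plan) analyses the balance point for Hypothesis 1.2 with a mixed model containing training condition, time (pre or post) and a person random effect. It then adds: "Similar models will test for group differences in active or sham IBT on other measures of hostile interpretation bias after training".

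For the Intent Attributions Questionnaire, also given only after training, the online-assessment section states a reason: "Because this scale can only be administered every six months, we are limited to a post-training assessment only". It also concedes that change on that scale cannot be assessed and that only arm differences can.

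**The concern.** A reduction needs a starting value, and none is collected on untrained faces. Three things follow.

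First, no adolescent has a change score on these faces, and neither arm has a mean change. A post-training gap between arms cannot show whether active training moved judgments toward happy, sham moved them toward angry, or both. Sham is itself a training condition, with feedback that reinforces the current balance point, so the gap is measured against sham and not against no training.

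Second, the model named for Hypothesis 1.2 cannot be carried over as written, because a measure taken at one time point has no pre/post term.

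Third, the between-arm test lacks a baseline on its own scale. The plan calls the study overpowered for IBT effects because they should be large, but it says itself that the existing evidence comes from trained faces. It gives no effect size or power for untrained faces.

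Unlike for the Intent Attributions Questionnaire, the plan gives neither a reason nor a caveat for the post-only timing of NimStim.

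**Working it through.** **1. Is there a pre-training NimStim assessment anywhere?** The assessment before IBT takes about 3 minutes. The Interpretation Bias Training Session text says it uses the prototypical male faces. The NimStim task takes 7.5 minutes, so it is not the same task. The visit table, the Visit 1 form lists and the online assessment contain no NimStim task. The post-only timing is read from the order of the Visit 2 text, since the NimStim sentence does not itself say when it is given. Nothing in the documents supports another order.

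**2. The plan's own Aim 1 figure.** For Hypothesis 1.1 the plan states 80% power for r = .25, N = 100, one-tailed .05. By Fisher's z: atanh(.25) × √97 − 1.645 = 2.516 − 1.645 = 0.871, and Φ(0.871) = 80.8%. It reproduces, but it concerns a correlation at baseline and does not bear on the untrained-face comparison.

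**3. What the post-only comparison estimates.** With outcome SD 1 and a true active-versus-sham effect of 0.5 SD, 20,000 simulated trials of 50 versus 50 gave a mean post-only difference of 0.50 at pre-post correlations of both 0.5 and 0.7. Under randomization it is unbiased for the between-arm effect.

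**4. What it cannot separate.** A post-training gap of 0.5 SD arises equally if active shifts 0.5 toward happy and sham stays put, if active stays put and sham shifts 0.5 toward angry, or if each shifts 0.25. Only the first matches Hypothesis 1.2.

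**5. Precision.** Inputs: n = 50 per arm (Specific Aims). Two-sided .05 and 80% power are assumed here, because the plan states none for this test. The pre-post correlation ρ is not in the documents and is assumed to be 0.3 to 0.7.

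- Post-only: solving the noncentral t power equation (98 df, noncentrality d × √(50/2)) for 80% gives d = 0.566.
- ANCOVA on a NimStim baseline: 0.566 × √(1 − ρ²).
- Change score: 0.566 × √(2(1 − ρ)).

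| Assumed ρ | Post-only | ANCOVA | Change score |
|---|---|---|---|
| 0.3 | 0.57 | 0.566 × 0.954 = 0.54 | 0.566 × 1.183 = 0.67 |
| 0.5 | 0.57 | 0.566 × 0.866 = 0.49 | 0.566 × 1.000 = 0.57 |
| 0.7 | 0.57 | 0.566 × 0.714 = 0.40 | 0.566 × 0.775 = 0.44 |

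The normal approximation gives 0.560 post-only and 0.535, 0.485 and 0.400 for ANCOVA. At one-sided .05 the post-only figure is 0.50.

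**6. Against a fairer comparator.** Every adolescent already has a pre-training balance point on the prototypical faces. If that correlated 0.5 with post-training NimStim (assumed), adjusting for it would already give 0.49. A NimStim baseline at ρ = 0.6 (assumed) gives 0.566 × √(1 − 0.36) = 0.45. The further gain is then 0.04 SD.

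**7. Visit time.** Stated task times sum to 3 + 18 + 3 + 7.5 = 31.5 minutes, taking the post-training prototypical assessment as 3 minutes like the first. Adding 7.5 gives 39 minutes, against a one-hour out-of-scanner visit. Setup and instruction time is not stated.

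**The case against.** A reader might infer that the trial cannot test generalization at all. The documents do not support that. Training is randomized, and section F already plans the active-versus-sham comparison on the other bias measures after training, which targets the average effect relative to sham. One qualification applies. Each arm fills by adolescents with acceptable data and baseline bias is not a minimization factor, so balance in the analysed set does not rest on randomization alone.

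A reader might also infer that exploratory Hypothesis 3.1 is damaged. It is not. Section F defines it with the balance point before and after training, which the trained-face task supplies, and plans no NimStim change score.

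Nor should chance baseline imbalance be counted as a separate harm. Its standard error is √(2/50) = 0.20 SD, and it is already contained in the standard error behind the 0.57.

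Three objections stand in part. The fall from 0.57 uses a comparator with no covariate, and step 6 shows a smaller gain. A pre-test means the NimStim faces are no longer new when generalization is tested. Equal exposure across arms does not rule out an interaction between that exposure and training. Placing 7.5 minutes of similar judgments before IBT also opens a gap between the assessment that sets the feedback and the training itself.

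Finally, the random-effect part of the model could survive if the four face identities supplied repeats. The time term could not.

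**Conclusion.** The point holds as a limit on interpretation and precision, and it does not invalidate the test. As designed, the trial can estimate the active-versus-sham post-training difference on untrained faces. It cannot measure reduction within a person or within an arm, so it cannot deliver the Summary's wording or the arm-specific form of Hypothesis 1.2 on those faces. The model for that comparison also needs its own specification.

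The precision cost is at most the fall from 0.57 to 0.54, 0.49 or 0.40 SD at assumed ρ of 0.3, 0.5 or 0.7, and less once the prototypical baseline is used. The conclusion rests on reading the Visit 2 text as a sequence, on 50 analysable adolescents per training condition, and on two-sided .05. The remedy is a cheap improvement worth making.

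**What to change.** Preferred: give the existing NimStim task before IBT in all four arms, after the prototypical-face assessment, so that the recorded balance point driving feedback is unaffected. Use ANCOVA (post-training NimStim balance point on training condition and pre-training NimStim balance point) for the between-arm test. Report change within each arm from a time-by-condition mixed model. Do not rely on that model's interaction alone for precision: with baseline means left free it behaves like the change score, which at ρ = 0.3 (0.67) is worse than post-only (0.57).

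Cost: a protocol amendment, 7.5 minutes per adolescent, some fatigue, the gap before training, and prior exposure to the test faces. Time in the two-hour in-scanner visit should be checked as well.

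If the task stays post-only: adjust the NimStim comparison for the pre-training prototypical balance point, and write out the single-time-point model in section F. Restate the Summary as an active-versus-sham post-training difference, and add the caveat already given for the Intent Attributions Questionnaire. This needs no new data collection.

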#### Assessment, Online, About one Week after IBT

The day before it is due, Drs. [name] or [name] will call the family to remind them to complete their follow up assessment. Drs. [name] or [name] will ask parents, “Do you have new concerns about your child since the training session?” The scales included in this assessment are the same as in the first visit, excluding the Tanner Scale. In addition, during the post-training assessment, adolescents will complete the Intent Attributions

Questionnaire, another measure of interpretive bias (10 minutes). Because this scale can only be administered every six months, we are limited to a post-training assessment only. Though we cannot assess IBT-associated changes in ratings on this scale, we can assess for both associations with irritability as well as differences in hostile attribution bias between those in the sham vs. active IBT groups.

For online assessments, adolescents will complete the following self-report forms:

1. Short Moods and Feelings Questionnaire (MFQ; 2 minutes)
2. Screen for Childhood Anxiety Related Emotional Disorders (SCARED; 8-10 minutes minutes)
3. Affective Reactivity Index (ARI; 2 minutes)
4. State-Trait Anger Expression Inventory-2 Child and Adolescent (STAXI-2 C/A; 5-8 minutes)
5. Intent Attributions Scale (10 minutes)

During this visit, caregivers will complete the following parent-report forms:

1. ARI (2 minutes)
2. SCARED (8-10 minutes)
3. MFQ (2 minutes)
4. SNAP-IV, items 1-40 only, (5-10 minutes)

Based on conducting similar online assessments at the NIMH, I anticipate this assessment to take approximately ½ hour for the adolescent and 15 minutes for their caregiver.

*Interpretation Bias Training Session.* The interpretation bias training session consists of an assessment of interpretation bias followed by trainings to shift the bias. A training session is depicted in Figure 1.

The assessment uses “prototypical” male happy or angry expressions. These were created combining twenty males from the Karolinska Directed Emotional Faces set. Thirteen linear morphs between these expressions generated a set of 15 stimuli, or “morphs,” on a continuum from happy (morph 1) to angry (morph 15). All trials consist of a fixation cross (1000ms plus 500-6000ms jitter, mean 1500 ms), morph presentation (150 ms), visual noise mask (250 ms), and response screen with a question mark (until response). Participants respond via keypress with “angry” or “happy.” Each morph of the full set is presented three times in random order. Data from this assessment is used to estimate each participant’s balance point, or the point along the morph continuum where the participant’s judgments change from predominantly happy to angry.

The training is divided into six blocks. Timing and stimulus presentation are the same as in the assessment block except that feedback was provided after each response. Because some will train during fMRI, which does not allow indefinite timing, the response screen timing is 1500 ms plus 500-6000 ms jitter, mean 2000 ms. Feedback will be presented for 1500 ms. Active training is designed to shift the balance point (measured by a pretraining assessment) toward happy judgments of ambiguous faces. Participants receive positive feedback for rating as happy (and negative feedback for rating as angry) two ambiguous morphs nearest to the balance point and had been rated as angry by the participant during the assessment. Patients will receive encouragement to attend for nonresponses, which are anticipated to be rare. Similarly, sham training provided feedback based on the balance point measured at the beginning of each session during the pretraining assessment block. In the case of sham training, the feedback is designed to reinforce, rather than shift, the current balance point. Regardless of what the baseline balance point is, feedback never encourages incongruent judgments of the three extremes on each end of the morph continuum. Both conditions present each morph twice in random order during each training block. There are six training blocks, consisting of 30 trials each lasting 2.7 minutes. In the scanner, each block will begin with an additional 9.2s of fixation for pre-magnetization and end with an additional 12s of fixation to measure BOLD return to baseline.

*Acquisition and Processing of Neuroimaging Data.* Adolescents will be scanned at the Brain Imaging Center at the University of Colorado Denver, using a 3.0 T Siemens Trio MR system with a 12-channel head coil. All adolescents will undergo either a real-scanner or mock-scanner acclimation procedure to orient them to the scanner and minimize loss due to motion artifact. BOLD sensitive echoplanar images with axial slices (3mm thick) encompassing the cerebrum and part of the cerebellum (TR/TE=2300/30msec FA=70 FOV=24cm, matrix=96x96). A T1-weighted MPRAGE structural image will be collected to assist with co-registration and normalization of functional images. All fMRI data will be pre-processed and analyzed using the Analyses of

Functional NeurolImages software (AFNI). Each adolescent's echoplanar images will be aligned using the first slice as a reference. Images will undergo diffeomorphic registration to the MNI template, resampled to 2.5mm^3 voxels, and spatially smoothed using a Gaussian kernel of 5mm full-width at half-maximum. Movement parameters from the realignment stage will be entered as covariates of no interest to control for movement and for censoring or 'scrubbing' at a threshold 1 mm Euclidean distance. Task events will be modeled using a using a gamma variate hemodynamic response function with duration modulation via AFNI's 3dDeconvolve. Adolescents with average motion per TR of >1 mm Euclidean distance before censoring or a nonresponse rate of >20% will be excluded.

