#### Randomization

Within 48 hours of Visit 1, Drs. [name] or [name] will determine if any exclusion criteria are met. This time allows Drs. [name] and [name] to consult each other or clarify information with the participants to achieve consensus for any unclear exclusionary diagnosis. If so, [name] will call the participants to thank for their participation, inform them of their exclusion, and cancel their second visit. Some exclusionary criteria are not stable, and it is likely the participants will be eligible during the study period. In that case, participants will still be

marked as a “Screen Failure,” in the consented, but not enrolled, category. However, they will be offered the opportunity to reschedule in the future. In this case, the participants will need to repeat visit 1.

During the pilot phase, eligible adolescents will not be randomized to a study arm, but will be invited to follow procedures for any arm. After pilot, eligible adolescents will be randomized for a 2 x 2 factorial, single blinded, randomized controlled trial, eligible adolescents will be assigned to one of four arms representing TRAINING (active or sham IBT) and SCANNING (in- or out-of-scanner IBT). First, scan ineligible patients will be assigned to out-of-scanner training. Second, randomization will use established minimization procedures (R packages randPack and/or randomizeR) to ensure the four arms are similar in terms of sex, age, socioeconomic status (SES), and IQ. The single blind is required so I may track adolescents with acceptable data. Acceptable behavioral data are at least 70% accuracy on extreme morphs (see [name] et al. for the development of this threshold) and, if applicable, scans of acceptable quality (see below). Allocation to any arm will end when the accrual goal of 25 adolescents with acceptable data have been reached for a total N=100. Since this is a small trial that is not intended to assess clinical efficacy, promoting power and ensuring balance across confounds outweigh the potential for allocation bias due to single-blinding or minimization procedures.

#### Training, Visit 2, Up to Day 7

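### A scan is excluded only when its mean motion passes the same 1 mm limit that censors one volume; no cap limits the censored share, and the group-level models omit motion

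*Combined protocol and SAP*

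**What the plan says.** The paragraph on acquisition and processing of neuroimaging data handles motion in three steps.

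- Within person: "Movement parameters from the realignment stage will be entered as covariates of no interest to control for movement".
- Per volume: the same parameters are used "for censoring or 'scrubbing' at a threshold 1 mm Euclidean distance".
- Per scan: "Adolescents with average motion per TR of >1 mm Euclidean distance before censoring or a nonresponse rate of >20% will be excluded".

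The Randomization section makes the scan rule part of accrual. Acceptable data require, for those scanned, "scans of acceptable quality (see below"), and the neuroimaging paragraph is where that pointer leads. The section continues: "Allocation to any arm will end when the accrual goal of 25 adolescents with acceptable data have been reached for a total N=100". It also explains that the trial is single-blind so that the investigator can track who has acceptable data.

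At group level, section F (Data Analysis Plan) tests hypotheses 2.2 and 2.3 with morph, pre-training ARI and training condition. Its candidate covariates are sex, age, SES, IQ, anxiety, depression, pubertal development and in- or out-of-scanner training. Neither list contains motion or the censored fraction.

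**The concern.** A limit that makes a single volume unusable is a weak limit for the average of all volumes. A participant can lose a large part of the time series and still pass, because the only motion test is the mean before censoring. The same sentence does limit loss from nonresponse, at 20%, so loss of data is recognised as a reason to reject a scan. Loss from motion has no such limit.

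Two things are at stake. First, imprecise scans count toward the 25 per in-scanner arm and are not replaced. Because acceptability is tracked by someone who knows the arm, a cut-off added later would be open to that knowledge. Second, the imaging hypotheses relate a neural measure to irritability. Within-person regressors and censoring do not remove differences between people in residual motion. If motion were related to ARI, the group-level models as written have no term for it.

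**Working it through.** **The plan's own figures.** The plan states no expected censored fraction, so there is none to reproduce. The nearest calculated figure is the imaging sample size of 50 (R² = .15, 80% power, p = .05). With r = √.15 = .387 and two-sided alpha .05, Fisher's z gives N = ((1.960 + 0.842)/atanh(.387))² + 3 ≈ 50.0. The figure reproduces and is not disputed here.

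**Scan length.** Each block lasts 2.7 min = 162 s, plus 9.2 s and 12 s of fixation, which gives 183.2 s. At TR = 2.3 s that is 79.7 volumes per block, or about 478 over six blocks.

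**What the rule lets through, with no distributional assumption.** These are two-level scans with mean = p × high + (1 − p) × low, where p is the share censored.

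| Share censored | High / low (mm) | Mean (mm) | Result |
|---|---|---|---|
| 1/3 | 1.5 / 0.3 | 0.70 | retained |
| 1/2 | 1.5 / 0.3 | 0.90 | retained |
| 80% | 1.1 / 0.2 | 0.92 | retained |

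Markov's inequality gives P(X > 1) ≤ mean. At a mean of 1 mm that is no limit at all.

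**Illustrative share for a scan near the limit (assumption).** The documents give no distribution of per-TR motion. The table shows P(X > 1 mm) under several right-skewed forms.

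| Assumed form | Mean 1.0 mm | Mean 0.9 mm | Mean 0.5 mm |
|---|---|---|---|
| Exponential, exp(−1/mean) | 36.8% | 32.9% | 13.5% |
| Lognormal, log-SD 0.5 | 40.1% | 32.2% | 5.1% |
| Lognormal, log-SD 1 | 30.9% | 27.2% | 11.6% |
| Lognormal, log-SD 2 | 15.9% | 14.6% | 8.9% |
| Half-normal | 42.5% | 37.5% | 11.1% |
| Gamma, shape 0.5 | 31.7% | 29.2% | 15.7% |
| Gamma, shape 2 | 40.6% | 34.9% | 9.2% |

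For means of 0.9 to 1.0 mm the range is about 15% to 43%. In the exponential case at 1.0 mm this is 0.368 × 478 ≈ 176 volumes. At a mean of 0.5 mm it falls to 5% to 16%.

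**What a group-level motion term can do.** Mean motion has one value per person, while the test of hypotheses 2.2 and 2.3 is a morph × ARI × condition interaction. When every morph is estimated in every person, a person-level main effect is orthogonal to contrasts between morphs. A simulation with 50 people and 15 morphs, in which motion was correlated with ARI and affected the signal, shows this. The interaction estimate was 0.10998 (SE 0.2471) both with and without the motion main effect. Only the person-level ARI effect moved, and there the covariate removed the bias. Where the motion effect differed by morph, a motion-by-morph term removed the bias in morph × ARI.

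**The case against.** The strongest reply is that the harm is not shown, and much of that reply stands.

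- **Censored share.** A reader might infer that retained scans typically lose about a third of their volumes. The documents give no motion distribution, and that figure describes a scan near the limit under particular assumptions.
- **Trials lost.** The two trained morphs are each shown twice in six blocks, which makes 2 × 2 × 6 = 24 trials. A reader might infer that 24 × 0.65 × 0.80 ≈ 12 remain after 35% censoring and 20% nonresponse. The plan does not support this. Censoring removes volumes, not trials; a trial of 162/30 = 5.4 s spans about 2.3 TRs, so one with a censored volume still contributes. The sum also stacks two worst cases, although nonresponse is expected to be rare. Nor are those trials clearly the only carriers of learning, since the planned models include generalization among stimuli.
- **Bias.** A reader might infer that motion would appear as the ARI effect under test. A motion–ARI link common to both arms and all morphs falls in the ARI main effect, not in the three-way interaction. No motion–ARI relation is documented.
- **Weighting.** A reader might infer that poor scans count equally with good ones. The plan says only mixed-effects models and does not state this.
- **Existing safeguards.** Scanner acclimation, an age range chosen partly to limit motion, and diagnostics for influential data all reduce the risk.

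None of these supplies a limit on the censored fraction. The safeguards make bad scans rarer but do not decide which ones count.

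**Conclusion.** The gap in the rule is real and follows from the text alone: a scan with half or more of its volumes censored can be acceptable and fill an accrual place. The 15% to 43% range depends on the assumed distributions and on a mean of 0.9 to 1.0 mm; it is a worst-case description. The absence of motion from the group-level models is also plain from the text. Its effect on the ARI results has unknown size and direction, because the documents report neither the motion distribution nor its relation to ARI. The point concerns hypotheses 2.2 and 2.3 and exploratory hypothesis 3.2. The Aim 1 tests do not use the imaging data. The change is modest and inexpensive; nothing here shows that the planned imaging results would be invalid.

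**What to change.** 1. In the neuroimaging paragraph, add a maximum fraction of censored volumes for an acceptable scan, fixed before arm or task effects are seen. The 20% already used for nonresponse is one option, but it was set for a behavioural criterion, so the sponsor should justify whatever value is chosen.
2. In section F, add mean per-TR motion as a covariate in the person-level tests: hypothesis 3.2, the region-of-interest analyses and ARI simple effects.
3. For hypotheses 2.2 and 2.3, include a motion-by-morph term or a named sensitivity analysis. A motion main effect alone cannot change the morph × ARI × condition estimate.
4. Report mean motion and censored fraction by arm and against ARI.

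The motion values are already produced in realignment, so the work is mainly wording. The costs are one or a few degrees of freedom and some failed scans that need replacement. If more irritable adolescents move more, a strict cap would remove some of them and narrow the ARI range. That trade-off should be weighed when the value is set.
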